
Recruitment: 40 subjects to be recruited over a 3-month period in SA using social media, i.e., Facebook and Instagram to recruit on-line sports betting gamblers and through the OPG Gambling Help Services throughout SA.

Design: this would be a 12-month single arm trial with all participants being offered CET. Participants would receive up to 10 sessions (30-60 mins) provided over 2 months and follow up for another 3 months. We will recruit until we have 40 people who have provided signed consent forms and baseline questionnaires. All will be offered the intervention. As for all psychological interventions, of the 40, a proportion will not attend a single session (~5%), some will attend a single assessment only session (~10%) and others only 1 assessment and 1-2 therapy sessions (~20%) leaving about 65% who attend 4 or more sessions. (ie one assessment + 3 therapy sessions). This provides a naturalistic comparison group ie 35% of the sample who received no or minimal intervention compared to the intervention group (65%) who we will define as having 'an adequate dose' of the intervention. We will also conduct a per

protocol analysis of those who completed all 10 sessions to see the effect of the full dose of the intervention.

Phase 2:

140 subjects will be randomised to intervention (CET) or control ie usual care, in a 2-arm parallel 26 month randomised controlled trial, each arm receiving up to 10 sessions over 12 weeks delivered by phone and/or videoconferencing. Each participant will be followed for 12 months post intervention to determine outcomes of gambling behaviour, problem gambling severity, anxiety, depression and work and social adjustment.

Consumer and Community engagement – investigators are encouraged to consult with [Consumer and Community groups](#) with the design of their research. Please outline any consultation that has occurred.

SGTS has an active consumer group led by [name] a former client of SGTS who has recovered from a gambling addiction. He is employed 0.1FTE by SALHN to provide support to gamblers about to start treatment and during treatment. He has provided input to the design of the workbook and will be asked to continue his current role in contacting participants in the trial during their therapy to provide education and support as well as obtain feedback on the acceptability of the intervention.

What are your outcome measures?

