Primary outcome. Phase 1: Outcome assessments will occur at baseline, post-treatment (12 weeks) and follow-up at 2-month post-treatment.

Phase 2: Outcome assessments will occur at baseline, post-treatment (12 weeks) and follow-up at 3 and 12-month post-treatment.

Primary outcome: The participant-rated primary outcome measure is the Victorian Gambling Screen (VGS) harm to self-subscale (Likert scoring 0, 1, 2, 3, 4; range 0-60); a score of 21 and above identifies a person as a problem gambler) relating to the person's experiences in the person's experiences in the previous 4 weeks.

Secondary outcomes: number of days spent gambling and amount of money spent per day gambling will be measured over the previous 1 month, PHQ-9 (depression) GAD-7 (anxiety). WSAS (work and handicap). Other gambling measures include the Gambling Urge Scale (GUS) where higher scores indicate greater urges to gamble with a range 0–42 and the Gambling Related Cognitions Scale (GRCS) which is a 23-item seven-point Likert scale that records the degree of agreement with common thoughts associated with gambling disorder.

Phase 1 Qualitative: Semi-structured interviews with purposefully chosen (age above and below 20, those who improved/recovered/those who dropped out/did not recover) 6 intervention participants and 2 therapists to determine recruitment barriers and enablers, acceptability and feasibility and any improvements to the intervention or delivery and recruitment. Of particular interest will be the on-line and social media strategies used to recruit non help seeking sports betters.

Project duration:

Phase 1 timeline: 2 months set up, 3 months recruitment, 6 months intervention (3 months during recruitment and another 3 months from end of recruitment), 2 months follow up, 2 months data analysis and write up. – total 12 months.

Phase 2 timeline: 2 months set up, 6 months recruitment, 9 months intervention (6 months during recruitment and another 3 months from end of recruitment) 12 months follow up, 3 months data analysis and write up – total 26 months.

Participant selection and activities

Explain how participants will be recruited or how their data will be selected (e.g. for a registry).

Describe sources and methods that will be employed in the identification and recruitment/selection of potential participants (e.g., clinics, referring doctors, adverts, and time periods) or of historical data (e.g. medical records, databases).

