The RA will contact the person to arrange a suitable time to go through the trial information, providing the patient information and consent form (PICF) electronically. If the person gives consent, they may sign this form electronically and return it electronically or print and scan or

print and post the form. They will also be asked to complete the baseline questionnaires at this or a subsequent session. These are returned as above. Once the questionnaires are completed the RA will arrange for the trial therapist to contact the person to commence CET (phase 1).

For phase 2, at this point the RA will contact the Clinical Trials centre to obtain the randomisation allocation. They will then provide the appropriate therapist information to contact the person to commence the first therapy session.

Intervention: CET. The first session includes asking the person to put Money Management in place ie ceasing or pausing credit card/phone/efpost access, cancelling phone and internet gambling accounts, arranging for a daily or weekly allowance managed by a significant other. All participants are given a standardised treatment rationale during their first session and checked if they agree to proceed with the treatment plan. They are also helped to define a problem statement and end of treatment goal. They receive a standard mental health and CBT assessment screening for co-morbid psychiatric disorders and risk to self or others.

The CET treatment is delivered in individual sessions and conducted according to a detailed manual which is adapted from one used previously in a randomised control trial ([name] et al. 2015). Treatment comprises up to 10 weekly 30-60-min sessions, though participants may have receive fewer or a greater number of sessions depending on the pace at which they moved through their graded cue exposure hierarchy.

During the second session an initial hierarchy of gambling cues is developed which is altered according to the clients' insights and responses throughout

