treatment. This is a collaborative process between therapist and participant and utilised cues such as their smartphone, images of sports betting websites and preferred sports, and videos of sporting matches. Exposure is graded up to watching a live sporting match online or on the television while holding a smartphone with betting account credits and habituating to the urge to gamble. For mixed gamblers, habituation tasks also include in vivo (live) exposure in a gambling venue holding money and habituating to the urge to gamble. Clients are encouraged to perform CET homework regularly between session. Once participants extinguish their urge response from a cue, they moved to the next task on their graded hierarchy.

Control (phase 2): Usual care: Up to 10 sessions described in a workbook will be provided of 30-60 minutes duration consisting of education about gambling risks and harms, the technology and psychology of gambling, skill vs computer algorithms which favour the gambling company, the psychology of intermittent reinforcement. Participants will be asked to monitor their gambling cognitions, gambling time and money spent/lost through use of a monitoring diary and assisted to set life recreational goals as alternatives to gambling.

All participants will be asked to complete questionnaires, provided on-line via email at the beginning of each treatment session as per usual care for gambling clients taking 10-15 minutes ie Gambling time and money spent, PHQ-9 depression (q 9 to check for suicidal behaviour), GAD7 anxiety and additional questionnaires as above at baseline (30-40 minutes), session 4, end of treatment session 10 and 2 month post treatment follow up (phase 1) and 3 month and 12 month post treatment (phase 2) .

For phase 1, 6 participants and 6 significant others will be asked to participate in a semi-structured interview of 15-30 minutes of the acceptability and feasibility of the recruitment process and intervention.

Participant follow up – how are participants monitored during the study?

Participants are followed up weekly at each therapy session and at 2 months follow up (phase 1) by the therapist both from use of questionnaire data and phone or video observation and clinical contact and for phase 2, at 3 and 12 months post treatment by the RA.

All participants are monitored through the clinical on-line data collection system PC-MIS and weekly therapist supervision sessions provided by CIs, [name], [name] and [name]

Consent

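### The post-treatment VGS has two conflicting timing rules, 12 weeks and session 10, with none for people who stop early or run late; the ten-session per-protocol set also conflicts with the flexible number of sessions

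*Protocol*

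**What the plan says.** The protocol times the post-treatment assessment in three places.

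- *What are your outcome measures?*, Phase 1: "Outcome assessments will occur at baseline, post-treatment (12 weeks) and follow-up at 2-month post-treatment". Phase 2 has the same 12-week point, then 3 and 12 months after treatment.
- *Participant commitment*: the additional questionnaires are due at baseline and then at "session 4, end of treatment session 10 and 2 month post treatment follow up (phase 1"), or at 3 and 12 months for Phase 2. The paragraph does not name the VGS; it refers back to the measures listed earlier, of which the VGS is the primary one.
- *Design* (Phase 1): sessions are "provided over 2 months and follow up for another 3 months".

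The number of sessions is not fixed. The CET description sets up to ten weekly sessions but allows "fewer or a greater number of sessions depending on the pace at which they moved through their graded cue exposure hierarchy". On enrolment, the Design paragraph says: "We will recruit until we have 40 people who have provided signed consent forms and baseline questionnaires". It then expects about 5% of the 40 to attend nothing, about 10% the assessment only, and about 20% the assessment plus one or two therapy sessions. That 35% is to serve as a naturalistic comparison group for the 65% with four or more sessions. The same paragraph adds a per "protocol analysis of those who completed all 10 sessions to see the effect of the full dose of the intervention".

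The analysis section makes the primary analysis intent-to-treat on all available data, with per-protocol and as-treated analyses secondary and weighted. Missing data are to be multiply imputed.

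**The concern.** A calendar rule and a session rule agree only for someone whose tenth session falls at week 12 and is also the last. For everyone else the protocol does not say when, or whether, the post-treatment VGS is collected. The people most affected are those who stop early, so under the session rule missingness of the primary outcome would follow attendance.

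Three uses of the data depend on this: the intent-to-treat analysis, the 35% versus 65% comparison (which needs outcomes from the 35%), and the Phase 1 change in VGS that *Expected outcomes* says will inform Phase 2.

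The per-protocol set raises a related problem. If the number of sessions depends on pace through the hierarchy, requiring all ten selects partly on pace of response.

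**Working it through.** **1. The protocol's own attendance figure.** Inputs are from the Design paragraph. 5% + 10% + 20% = 35%; of 40 that is 2 + 4 + 8 = 14, leaving 26 (65%). The three categories are 0, 1 and 2–3 sessions, so all 14 stop before session 4. The figure reproduces.

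**2. The timing statements side by side.** Two months is 2 × 52/12 = 8.7 weeks, and 12 weeks is 12 × 12/52 = 2.8 months.

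| Place | End of treatment or post-treatment point | Last Phase 1 follow-up |
|---|---|---|
| Design, Phase 1 | 2 months | 2 + 3 = 5 months |
| Outcome measures, Phase 1 | 12 weeks (2.8 months) | 2.8 + 2 = 4.8 months |
| Participant commitment | session 10 | 2 months after treatment |
| CET description | up to ten weekly sessions, or fewer, or more | – |

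Ten weekly sessions span nine intervals, so with no missed week session 10 falls 9 weeks after session 1. That is close to 2 months and three weeks short of 12. The Project duration section (three months of intervention after recruitment closes, then two months of follow-up) matches the outcome section. The Phase 1 totals nearly agree; the disagreement is over where treatment ends. In Phase 2 the Design paragraph and the outcome section both say 12 weeks, so only the session-10 wording conflicts there.

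**3. What each rule leaves missing in Phase 1.** If the VGS goes to everyone at 12 weeks, the schedule leaves 0 of 40 without it. If it is collected only at session 10, the number missing is 40 minus the number who reach session 10. The protocol does not give that number, so a range is assumed:

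| Reach session 10 (assumed) | No post-treatment VGS |
|---|---|
| 26 (all who reach session 4) | 14 (35%) |
| 20 | 20 (50%) |
| 13 | 27 (67.5%) |
| 8 | 32 (80%) |

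The minimum is therefore 14. Those 14 would also have no session-4 form, so baseline would be their only VGS before follow-up.

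**4. The follow-up origin.** The 2-month follow-up is not tied to a session number, but its starting point is undefined for someone who stops early. For a person stopping at week 2, counting from the last session gives 2 + 8.7 = 10.7 weeks, before a 12-week post-treatment assessment. Counting from the 12-week point gives 12 + 8.7 = 20.7 weeks. The text allows either.

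**5. Per protocol.** Someone who completes the hierarchy in seven sessions has followed the CET description but is outside the ten-session set. Someone slower, who needs all ten, is inside it.

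**The case against.** The strongest reply is that the outcome section already fixes the assessment at 12 weeks and nothing makes it conditional on attendance. Several features support that reading. All participants are to be asked for questionnaires, and these go out online by email. The ethics section distinguishes session forms from trial data collection points. Willingness to give follow-up data is an inclusion criterion, and the 35% versus 65% comparison presupposes outcomes from the 35%. The session-10 wording may simply mean the nominal end of treatment. The model takes time as continuous, imputation is planned, and Phase 1 tests no hypothesis.

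Much of this stands. A reader might infer that the primary outcome is missing by design and intent to treat is defeated; the protocol does not support that, because it follows only if the session schedule overrides the 12-week rule. Nor can it be said that everyone off the ten-session path lacks the form: people who go beyond ten sessions do reach session 10, which is just not their end of treatment. Applying 35% to Phase 2 to get 49 of 140 without a VGS is also unsupported, since the Phase 2 figure is a treatment drop-out rate not defined by session number.

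The reply does not remove the conflict. The 12 weeks has no stated origin, and the more operational section ties the forms to sessions. A continuous-time model can use unequal dates but not values never collected. Imputation for early stoppers would lean heavily on people who stayed.

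**Conclusion.** The concern holds as a contradiction to be reconciled before recruitment. The post-treatment VGS has two timing rules and no rule for those who stop before, or continue past, session 10. If the session rule is followed, at least 14 of 40 in Phase 1 have no post-treatment VGS, plus an unknown number stopping at sessions 4 to 9. If 12 weeks is applied to everyone from a stated origin, the schedule itself causes none. The figure of 14 rests on the protocol's expected attendance and on reading the reference to earlier questionnaires as including the VGS. The conflict over treatment duration is confined to Phase 1.

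The per-protocol definition is inconsistent with the flexible number of sessions, but this affects only a secondary analysis. A reader might infer that early responders are dropped from the trial's results. They are not: the primary analysis keeps them, and the group with four or more sessions keeps those who attended that many. Nor does the protocol show which way the ten-session analysis would be biased, because that set also excludes drop-outs.

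**What to change.** - In the outcome section and under Participant commitment, state that the VGS set is sent online to every participant at 12 weeks from baseline (Phase 1) or from randomisation (Phase 2), whatever their attendance. Set later follow-ups at fixed times from the same origin.
- Keep the session-4 and session-10 forms as process data.
- The sponsor must reconcile the Phase 1 durations (2 months plus 3 months in Design, 12 weeks plus 2 months in the outcome section). Which treatment length is intended is the investigators' decision.
- Either count recorded completion of the hierarchy as per protocol, or label the ten-session analysis a descriptive dose subgroup selected on pace of response. Redefining per protocol as four or more sessions would only duplicate the existing adequate-dose group.

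The cost is protocol wording, scheduled invitations through the email route already in use, and one extra emailed form for people who stop early. If the full set is also kept at session 10, participants whose tenth session falls away from week 12 complete it once more (30–40 minutes by the protocol's estimate). For anyone still in treatment at week 12, the assessment describes status at that date rather than after treatment; the report should say so.

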Suicide risk is managed by a screening question (q9 of the PHQ-9) at the start of each session, if active suicidal thoughts or plans are detected the therapist will abandon the therapy content and specifically focus on further assessment of suicidality and plans for the person to access help through the local mental health service, GP, Emergency Department or state mental health triage phone number. Furthermore, a partner or significant other is advised with the participant's approval to be involved in the supporting the participant in the study and they will be asked to monitor distress and suicidality and provided with options for help seeking as appropriate. As the PHQ-9, including q9 which asks about suicidal ideation is administered by the therapist at each session (both intervention and controls) any suicidality will be addressed by the therapist. As

part of usual care, therapists use mobile phone contact via text messaging as 2-way communication between sessions so the participant may contact the therapist if they are distressed. This will not be initiated by the therapist unless they are concerned about the participant based on the session they have just had or text or voice messages received from the participant which indicate distress or suicidality.

Benefits – please identify and explain the expected outcomes and benefits of the study

There will be benefits to the individual involved in the study as per the published case studies by having their gambling urges either eliminated or under control and improved finances and quality of life. If the studies show improved outcomes by a remotely delivered intervention people with sports betting addiction across Australia and internationally could benefit by improved access to an effective treatment.

Individuals consenting to the study will receive a supermarket gift voucher of \$30 once baseline questionnaires are completed and at the final follow up data collection point (ie \$60 per person) to compensate for their time to be involved with the study.

Does a dependant or unequal relationship exist between the participant and the researcher?

Please refer to the National Statement 4.3 for advice and guidance on how to manage this.

Yes -

How will the dependant / unequal relationship be managed? [Click here to enter text.](#)

No

Data management – as required in addition to that outlined in your HREA

As per the National Statement 3.1.45, researchers must have a data management plan in place.

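### An unexplained missed session is not among the stated grounds for therapist-initiated messaging, and no suicide-risk check is set for a participant who stops attending

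*Protocol*

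**What the plan says.** Under *How will any risks be managed?* the protocol states: "Suicide risk is managed by a screening question (q9 of the PHQ-9) at the start of each session". A positive answer leads the therapist to set the session content aside, assess further and arrange help. The same section describes two-way text contact between sessions, which a distressed participant may use. Of contact started by the therapist it says: "This will not be initiated by the therapist unless they are concerned about the participant based on the session they have just had", or by "text or voice messages received from the participant which indicate distress or suicidality". With the participant's approval a significant other is also involved: "they will be asked to monitor distress and suicidality and provided with options for help seeking as appropriate".

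Other sections add general cover:

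- *Consumer and Community engagement* gives a peer worker the role of "contacting participants in the trial during their therapy to provide education and support".
- *Participant follow up* places every participant under PC-MIS monitoring and weekly therapist supervision.
- *Participant commitment* puts a risk screen and money management in the first session.

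The Phase 1 *Design* paragraph expects about 5% to attend nothing, about 10% to attend the assessment alone, and "others only 1 assessment and 1-2 therapy sessions (~20%) leaving about 65% who attend 4 or more sessions".

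**The concern.** Under *Ethical considerations* the protocol names suicidality after large losses as a risk inherent in gambling disorder. It argues that the trial lowers this risk because trained therapists assess it at every session. That argument holds only while the participant attends.

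A session that is missed without explanation is an event staff can see, and it may follow a heavy loss. Yet the messaging rule lists two reasons for the therapist to make contact, and absence is neither. A therapist who follows the text literally has no stated ground to text a participant who seemed well last week, did not appear this week and has sent nothing. At stake is the safety of a group whose existence the protocol itself predicts. The validity of the results is not affected.

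**Working it through.** No sample size or power figure is in dispute. The check sets the provisions side by side, then sizes the group and the interval.

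**1. Does any provision respond to absence?**

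- Question 9 screen: given at sessions, so it needs attendance.
- Emailed session questionnaires and the session 4 set (*Participant commitment*): tied to sessions.
- Therapist-initiated messages: need concern from the session just held, or a received message showing distress.
- Participant-initiated texts: need the participant to act.
- Peer worker: contact during therapy for education, support and feedback. No risk check is stated.
- PC-MIS and weekly supervision: cover everyone. No action on non-attendance is stated.
- Significant other: not staff, and conditional on approval.
- First-session risk screen: cannot detect later deterioration.

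**2. Apply the messaging rule to a case.** There was no concern at the last session, a large loss follows, the participant sends no message and misses the next session. Concern from the session just held: no. Message showing distress: no. Neither ground is met.

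**3. How many people?** Inputs are the *Design* percentages and n = 40.

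- The plan's own figure: 100% − 5% − 10% − 20% = 65%, and 0.65 × 40 = 26 who attend four or more sessions. It reproduces.
- Never start: 0.05 × 40 = 2. *Participant commitment* already has the therapist contact them to begin.
- One session only: 0.10 × 40 = 4.
- Two or three sessions: 0.20 × 40 = 8.
- Start and stop before session 4: 4 + 8 = 12.

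Some of the 12 will withdraw formally or will have caused concern at the last session, which already permits contact. Against that, any of the 26 who stop later are not counted. The documents give no number for those who go silent.

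**4. How long until the next scheduled screen?** Assume session k falls in week k. Then gap = week of post-treatment assessment − week of last session, for a last session between 1 and 3.

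- Assessment at 12 weeks (*What are your outcome measures?*): 12 − 3 = 9 to 12 − 1 = 11 weeks.
- Assessment at the end of the 2-month treatment period (*Design*; 2 months = 8.7 weeks): 8.7 − 3 = 5.7 to 8.7 − 1 = 7.7 weeks.
- Assessment at session 10 (*Participant commitment*): 10 − 3 = 7 to 10 − 1 = 9 weeks if sent in week 10 regardless of attendance. If it truly depends on session 10, a drop-out does not reach it and the next scheduled point is the follow-up two months after treatment.

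Every reading gives several weeks, but the protocol does not settle which applies.

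**The case against.** The strongest reply is that the restrictive sentence concerns text messaging between sessions and nothing else. It says nothing about telephoning someone who missed an appointment, rebooking, or contact by the research assistant, peer worker or supervisors. Weekly supervision and PC-MIS cover all participants, so a non-attender could well be noticed and called. Therapy follows a detailed manual within an established service, and that manual, which is not shown, may already say what to do after a missed session. On this view the protocol is merely silent on a point usually handled by service procedures.

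Much of this stands. A reader might infer that the protocol forbids any follow-up of a non-attender, or that such people are left unmonitored. The documents support neither reading, since the rule covers one channel and the general cover does not lapse.

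What remains is narrower. On that channel the protocol is not silent: it states a restrictive rule, and the rule leaves out the one warning sign that silence produces. If the manual does set a missed-session step by text, the protocol sentence conflicts with it. If the step is by telephone, the protocol should refer to it.

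It is also fair to object that outreach could change attendance, which is itself a Phase 1 feasibility outcome. That is a cost to report and does not justify leaving the rule as it is.

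**Conclusion.** The point holds in this limited form. As written, an unexplained missed session is not a ground for therapist-initiated messaging, and nothing else in the protocol sets a risk check for it. About 12 of 40 in Phase 1 are expected to start and then stop before session 4, on the protocol's rounded planning percentages.

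Two stronger readings should be resisted:

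- A reader might take 12, or the 0.35 × 140 = 49 implied by the Phase 2 drop-out allowance, as the number of people left at risk. The first counts only early stopping and the second is a sample-size allowance. Neither measures silence or risk.
- A reader might quote 9 to 11 weeks as the length of the gap. That rests on the 12-week timing and on weekly sessions, and the protocol's other two timings give different answers.

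This is a cheap improvement to patient safety. It does not affect the analysis, and confidence is moderate because the treatment manual is not available.

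**What to change.** Amend the messaging sentence under *How will any risks be managed?* so that an unexplained missed session or stopped attendance is also a reason for the therapist to make contact. The contact should include a brief risk check (question 9 or an equivalent) and lead to the response already described if positive. Record the contact, the check and its result in PC-MIS. Apply the rule identically in both Phase 2 arms, and exempt anyone who withdraws or declines contact.

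Costs, assuming one or two contacts per person at 10 to 15 minutes each:

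- Phase 1, counting 12 + 2 = 14 people: 14 × 10 min = 2.3 hours to 28 × 15 min = 7.0 hours.
- Phase 2, using 49 as a rough planning count: 49 × 10 min = 8.2 hours to 98 × 15 min = 24.5 hours.

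Later stoppers in Phase 1 and isolated missed sessions add to this. Existing therapists can do the work. The change is a protocol amendment and must be reported to the lead ethics committee (*Post approval monitoring and reporting*).

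The main downside is a possible small rise in attendance. Each person who returns and reaches four sessions moves the adequate-dose group by 1/40 = 2.5 percentage points, for example from 26/40 = 65% to 27/40 = 67.5%. The log does not remove this effect, so Phase 1 completion should be reported alongside the number of contacts made and the number who returned after one.
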